The specific aims of this pilot project are:

1) To evaluate the feasibility of studying whether implementation of family gardens paired with a nutrition intervention program in rural Guatemala will lead to improvements in maternal and child dietary diversity, child growth and household food insecurity compared to a nutrition intervention program alone.

2) Evaluate the implementation of the intervention through the Reach Effectiveness Adoption Implementation Maintenance (RE-AIM) framework.

We hypothesize that by augmenting a standard nutrition intervention with improved household food access through a garden intervention, child growth, dietary diversity and food security will improve compared to outcomes with the nutrition intervention alone.

2. Background

Children in Guatemala are at high nutritional risk, with a 47% prevalence of stunting (chronic malnutrition) and low full coverage with vitamin A supplements (UNICEF 2016). Only half of Guatemalan children receive a minimum acceptable diet (according to World Health Organization criteria measuring dietary diversity and meal frequency) from 6-23 months (UNICEF 2016). The indigenous Mayan population is disproportionately affected by poverty, food insecurity and malnutrition, with the prevalence of chronic malnutrition reaching as high as 70% in rural areas.

Wuqu' Kawoq/Maya Health Alliance (MHA) has conducted several studies to determine what nutrition interventions really work to prevent and treat chronic malnutrition. As a result of these studies, MHA established a home-based nutrition program whose goal is catch-up growth, improvement of minimum dietary diversity, minimum meal frequency, and minimum acceptable diet and increased caregiver knowledge. In a 50-child pilot, this intervention resulted in a mean change in height for age Z score (HAZ) from -3.67 ± 0.99 to -3.37 ± 0.89 over 6 months and an increase from 15-21% on minimum acceptable diet. In a subsequent RCT of this intervention, a trend toward improved growth at 6 months was observed, although the change was not statistically significant. However, minimum dietary diversity and minimum acceptable diet both improved significantly (risk difference 16.9 and 15.9%, respectively). The intervention also resulted in improved daily intake of legumes, eggs, and vitamin A rich fruits and vegetables (risk difference 16.5, 10.4, 12.7% respectively) (Martinez et al, 2018).

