Agriculture is a major economic activity in Guatemala, with 70% of families working in this sector. Family agriculture has many obstacles, including lack of access to land and the expansion of cash crop (e.g., sugar cane, African palm) plantations. Most of the food that is grown locally is exported, rather than being used for local consumption.

Public and private organizations in Guatemala have worked to promote the production of food for consumption. However, very few of them have measured the impact of agricultural initiatives on nutritional status. Moreover, this is the first study in North Tecpán to evaluate the potential impact that adding a home food production (for

PROTOCOL TITLE:

Evaluating a family-based nutrition and garden intervention in rural Guatemala

consumption) component to a health-oriented nutrition program can have on maternal and child diet quality and nutritional status and household food security.

3. Study Design

This is a quasi-experimental study with an intervention group and a nonrandomly selected control (standard care) group.

- The *standard-of-care group* will consist of subjects recruited from Maya Health Alliance's nutrition program in prioritized communities of *North Tecpán, Chimaltenango, Guatemala*. Subjects in the standard care group will receive the current standard child nutrition care (growth monitoring, deworming medication, micronutrient supplementation, nutrition education classes and home visits).
- The *intervention group* will consist of subjects recruited from MHA's nutrition program in prioritized communities of *San Andrés Semetabaj, Sololá, Guatemala*. Subjects in the intervention group will receive the standard child nutrition care plus an additional agriculture component (agriculture education classes, supplies to build a home garden near the family home and on-going agricultural support).

A quasi-experimental design was selected because it was determined that household level randomization would be culturally and logistically difficult.

Both sites are rural. The intervention and control communities are 90 minutes apart by car and have similar prevalence of chronic malnutrition in children and similar sociodemographic characteristics (education levels, economic activity, health services, school access and food access).

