- At least one caregiver willing to provide written informed consent
- Caregiver of a child enrolled in the study, including women who may be pregnant
- Planned residence in the study area for the next 18 months

Exclusion criteria are:

- Children with acute malnutrition (weight for length Z scores of ≤ -2.0)
- Children with a severe medical illness that affects growth (e.g., heart disease, kidney disease, genetic condition) as determined by a MHA/Wuqu' Kawoq staff physician.
- Caregivers with cognitive impairments that prevent them from being able to provide informed consent

Children who are ineligible for enrollment in the research study will receive standard care (the home-based nutrition intervention) from MHA.

5. Number of Subjects

The study will enroll 140 children and their primary caregivers into two study groups: standard-of-care (n=70 children and 70 caregivers) and intervention (n=70 children and 70 caregivers).

6. Study Timelines

Five to ten families per month will be enrolled into the study from each study community. We anticipate that recruitment will take ~7-14 months.

The research team will have contact with enrolled participants over the course of 18 months. The primary study data collection time points will be at 0 months (enrollment), 6 months (end of standard of care/nutrition intervention), 12 months, and 18 months. It is anticipated that each of these study data collection visits will last approximately 1 hour,

PROTOCOL TITLE:

Evaluating a family-based nutrition and garden intervention in rural Guatemala

for a total of 4 hours. In addition to that, for the *intervention group only*, data will be collected at the first monthly agricultural home visit and at one additional agricultural home visit approximately 4 months thereafter. Each of these agricultural home visits will last approximately 1 hour for a total of an additional 2 hours. Combined, the total data collection time for the participant in the *intervention* group will be 6 hours.

The duration of the study interactions with the children and their caregivers is as follows:

- Standard child nutrition care (received by both groups) will last 6 months and will include nutrition classes for 5 weeks and one home visit a month. Standard nutrition care will involve approximately 16 hours of contact with MHA clinical personnel.

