- The add-on agricultural/garden intervention (received by the intervention group only) will last 8 months and will include monthly agricultural classes and monthly home visits. The agricultural/garden intervention will involve approximately 16 hours of contact with MHA agricultural personnel, in addition to the time dedicated to the standard nutrition intervention.

A select number of participants (approximately 10) in the *intervention group* only will be asked to participate in one of two focus groups, approximately 90 minutes in length, between 6 and 9 months after the first enrollment. Participation in the focus groups will be fully voluntary and will not have any impact on the services or benefits received by the participants.

A small number of community leaders and Wuqu' Kawoq staff will be asked to participate in interviews, approximately 90 minutes in length, between 6 and 9 months after the first enrollment. Participation in the interviews will be fully voluntary.

The expected total duration of the study is approximately 3 years from the date of IRB approval.

7. Study Endpoints

The primary endpoints of this study are changes in the prevalence of:

- *Adequate diet quality*, as assessed by the World Health Organization (WHO) Infant and Young Child Feeding Indicators (IYCFI) (WHO, 2007) minimum dietary diversity, minimum meal frequency, minimum acceptable diet) for children and the Minimum Dietary Diversity for Women (MDD-W) indicator for caregivers. (FAO 2016)
- *Household food insecurity*, as assessed by the Global Food Insecurity Experience Scale (household referenced) (FAO 2017)

Secondary endpoints of the study include changes in: child length-for-age Z-score; child weight-for-age Z-score; child weight-for-length Z-score; child prevalence of stunting, wasting and underweight; and household total crop species diversity.

PROTOCOL TITLE:

Evaluating a family-based nutrition and garden intervention in rural Guatemala

This study involved no more than minimal risk, so no safety endpoints are specified.

8. Research Setting

The study will be conducted in prioritized communities of North Tecpán, Chimaltenango and San Andrés Semetabaj, Sololá (see additional details in **Section 3. Study Design**). These are rural Mayan language speaking communities where MHA has been working providing primary care and nutrition services for several years. MHA collaborates closely with multiple other NGOs as well as Ministry of Health staff in the region.

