MHA has a dedicated research office located in Tecpán, close to the study communities. The office has dedicated file storage cabinets for research documents, high-velocity internet, dedicated full-disc encrypted phones and computers, statistical software (STATA), and

PROTOCOL TITLE:

Evaluating a family-based nutrition and garden intervention in rural Guatemala

online HIPAA-compliant file servers and a REDcap server. The study budget includes the purchase of a new vehicle for use by the study team. An IT technician and comptroller will provide support to the project as needed.

MHA will provide usual care for treatment of severe medical illness identified during the screening/recruitment phase.

10. Prior Approvals

The protocol is approved by the MHA IRB.

11. Multi-Site Research

N/A – this is not a multi-site study

12. Study Procedures

This study will be conducted in two different sites. These are rural, Mayan language-speaking areas where MHA has been working for several years to provide primary care and child nutrition services.

This is a quasi-experimental study with an intervention group and a non-randomly selected control (standard-of-care) group.

The *standard-of-care group* will consist of subjects recruited from Maya Health Alliance's nutrition program in prioritized communities of *North Tecpán, Chimaltenango*.

The standard-of-care child nutrition services include:

- Intake visit with research nurse to assess basic health history, demographics, WHO IYCFI, FIES and MDD-W for women
- Monthly growth monitoring
- Monthly micronutrient supplementation
- Deworming medication (every 6 months)
- Monthly home visits by community health worker (CHW) to provide individualized growth assessment to mothers
- Nutrition education classes with CHW (nutrition during pregnancy, breastfeeding, complementary feeding, chronic and acute malnutrition, hygiene and nutritious recipes)

The *intervention group* will consist of subjects recruited from MHA's nutrition program in prioritized communities of San Andrés Semetabaj, Sololá. The intervention group will receive all standard-of-care child nutrition services as described above, plus:

- Agriculture education classes with the study agronomist (home garden package, assessment of plant production, weed and pest control, water access, etc.)
- Home garden supplies including seeds and/or seedlings

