- Monthly home visits from a study agronomist to provide assistance to build a garden near the family home and on-going support throughout the study

PROTOCOL TITLE:

Evaluating a family-based nutrition and garden intervention in rural Guatemala

Study data will be independently collected by a study nurse for all enrolled subjects at 0, 6, 12 and 18 months:

- Basic health history and demographics Appendix A
- Child weight and length/height Appendix B
- Household Quick Poverty Score (QPS) Appendix C
- Food Insecurity Experience Scale (household) Appendix D
- WHO Infant and Young Child Feeding indicators (child) Appendix E
- MDD-W Indicators (caregiver) Appendix F
- Agriculture Inventory Survey (household) to measure crop diversity and crop utilization Appendix G

Note that child weight and length and WHO IYCFI are already routinely collected as part of evaluation data for the standard-of-care nutrition services.

Additional data will be collected by the study agronomist for the *intervention group only* during the first agricultural home visit and at one additional agricultural home visit approximately 4 months thereafter:

- Agricultural Home Visit Baseline Survey (Baseline Agricultural Practices; Gardening Experience and Motivation) Appendix H
- Agricultural Home Visit Follow-up Survey (Adoption of Methods; Level of Home Garden Maintenance; Hours Worked in Home Garden) Appendix I

13. Data Analysis

Descriptive statistics for each group will be calculated using Stata (StataCorp, College Station, Texas). Family poverty scores will be calculated with a validated numerical scoring system commonly used in Guatemala. Changes in primary and secondary study outcomes will be compared between study groups using the chi-square test, paired t-tests (or the non-parametric equivalent) and linear and logistic regression as appropriate.

Within the intervention group, the rate of overall adoption will be compared descriptively across various demographic groups, and changes in primary and secondary outcomes will also be compared descriptively between adopters and non-adopters. Focus groups and interviews will be coded and analyzed thematically using select constructs from the Consolidated Framework for Implementation Research (CFIR) as a framework.

This is a pilot study to determine the feasibility of a garden intervention and to generate an initial effect size estimate for future, well-controlled studies. As such no formal power analysis will be performed.

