Another potential risk from the study is that it might cause conflict between the study communities. This could occur because caregivers receiving the nutrition intervention might learn that others are also receiving the additional garden component. We attempt to minimize this risk by recruiting the intervention families from a different community than we recruit the standard-of-care families.

Finally, there is the potential of accidental disclosure of protected health information. Please see **Section 16. Data Management/Confidentiality** for procedures to minimize this risk.

19. Potential Benefits to Subjects

Individuals in both groups may benefit directly. Both groups will receive micronutrient supplementation, deworming medication, home visits and nutrition education, which we anticipate will have positive outcomes on diet quality, catch-up growth, decreased rates of severe stunting, and promotion of cognitive and motor development.

The agriculture intervention group will receive supplies to build a garden, home visits and agricultural education. We anticipate that this will increase their knowledge as well as food availability for their family, even after the study has finished (as the families will keep their garden supplies).

Over the long term, reversing the ill effects of stunting and food insecurity also contributes to improved school performance, adult earning potential, and reduced incidence of adult non-communicable diseases.

This study will help to fill an identified gap in research at the nexus of nutrition, food production and health. Specifically, this work will provide evidence about measurement and indicators used to evaluate diet quality, health impacts and food security when providing nutrition interventions paired with agriculture interventions in rural communities in the highlands of Guatemala.

The implementation evaluation component of this study will provide new knowledge about how various caregiver, provider and community-level factors can affect the implementation of a home gardens program for malnutrition, giving valuable insights into how and why the intervention achieved the level of success that it did.

In this way, the study will help create a functional integrated nutrition and agriculture model that can be used by other organizations who are working or want to work in the treatment and prevention of malnutrition, while offering an understanding of the implementation challenges that

PROTOCOL TITLE:

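### Study group coincides with site, yet Section 13 lists a within-group test for comparing groups, fixes no regression of change, makes no allowance for community, and does not say that garden and site cannot be separated

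*Combined protocol and SAP*

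**What the plan says.** Section 3 describes a quasi-experimental study with a control group that was not randomly chosen. It explains that randomising households was judged culturally and logistically difficult. Section 12 states "This study will be conducted in two different sites", with the control group from North Tecpán and the garden group from San Andrés Semetabaj. Section 18 shows that the separation is deliberate: the risk of conflict is reduced by "recruiting the intervention families from a different community than we recruit the standard-of-care families". On comparability, Section 3 says "The intervention and control communities are 90 minutes apart by car and have similar prevalence of chronic malnutrition in children and similar sociodemographic characteristics", without figures.

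Section 7 begins "The primary endpoints of this study are changes in the prevalence of" and lists child and caregiver diet indicators and household food insecurity. Section 6 sets visits at 0, 6, 12 and 18 months and names none as the main one.

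The between-group analysis in Section 13 is a single sentence: changes in the outcomes will be "compared between study groups using the chi-square test, paired t-tests (or the non-parametric equivalent) and linear and logistic regression as appropriate". Section 12 collects demographics and a household poverty score, and Section 13 says the score will be calculated, but neither says that they will be used for adjustment. No section mentions a community term or clustered standard errors. Section 13 describes a pilot meant to "generate an initial effect size estimate for future, well-controlled studies", with no power analysis.

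**The concern.** Three things meet here.

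- **The comparison.** The question is whether change differs between two groups. A paired t-test answers whether one group changed. If each group is tested separately and only one result is significant, that can be mistaken for a group difference. Linear or logistic regression could estimate the right quantity, but the plan does not say which outcome form, covariates or visit.
- **Precision.** Families in the same community share markets, water, health workers and classes. An analysis that treats them as independent gives intervals that are too narrow if outcomes are correlated within communities.
- **Interpretation.** With one site per group, any difference between the sites is part of the estimate. No model fitted to these data can remove it.

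The effect size is a stated product of the study. If it passes to a later trial as the garden effect, with an interval that ignores place, that trial may be planned on the wrong figure.

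**Working it through.** **The plan's own figures.** The sample of 70 per group cannot be reproduced, because no error rate, power or effect is given. The recruitment time can. Section 6 says "Five to ten families per month will be enrolled into the study from each study community. We anticipate that recruitment will take ~7-14 months", and 70/10 = 7 months, 70/5 = 14 months. This works only if a study community means the whole of one group. Section 3 speaks of several communities in each area, so the number per group is unknown.

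**Degrees of freedom for site.** Two sites minus two groups = 0. Between-site variation cannot be estimated.

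Everything below rests on assumed inputs and shows possible size only.

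**Clustering.** Design effect DE = 1 + (m − 1) × ICC, with m families per community. True error of a nominal 5% test = 2 × [1 − Φ(1.96/√DE)]. Both m and ICC are assumed.

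| m | ICC | DE | Error |
|---|---|---|---|
| 5 | 0.01 | 1.04 | 5.5% |
| 10 | 0.02 | 1.18 | 7.1% |
| 10 | 0.05 | 1.45 | 10.4% |
| 10 | 0.10 | 1.90 | 15.5% |

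In simulation with 7 communities of 10 per group, the naive test had 7.0%, 10.0% and 15.9% error at ICC 0.02, 0.05 and 0.10. A t-test on community means had 5.0%, 4.8% and 5.1%. With 2 communities of 35 per group and ICC 0.05, the naive test had 23.2%, ordinary cluster-robust errors 11.9%, and community means 5.1%. This is why a small-sample correction is needed.

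**Paired tests read side by side.** Section 2 reports, for a pilot of the nutrition programme that both groups receive, "an increase from 15-21% on minimum acceptable diet". Suppose both groups of 70 truly change from 15% to 21%, so that there is no garden effect, with an assumed correlation between visits of 0.1, 0.3 or 0.5. A paired t-test then has power p of about 16%, 18% or 23% in each group. Exactly one group is significant with probability 2p(1 − p), about 27%, 30% or 35%. With the exact McNemar test, better suited to a binary indicator, the range is about 20% to 27%.

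**Baseline gap.** This uses length-for-age Z, a secondary endpoint, with the SDs 0.99 and 0.89 from Section 2's pilot. For an assumed correlation of 0.7 to 0.9, the slope is r × 0.89/0.99 = 0.63 to 0.81. An assumed gap of 0.25 Z between sites gives 0.25 × (1 − slope) = 0.09 to 0.05 Z. The change score is biased by this amount if both sites regress to one line, and the baseline-adjusted estimate if the gap is stable. Neither is safe alone.

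**Season against age range.** Take a 12-month sine wave with peak-to-trough swing S, common to both sites, and enrolment spread evenly from a common start. The largest shift in the between-group difference in 0–6 month change is 0 at equal pace, 0.27 × S for 8 against 10 months of recruitment, and 0.51 × S for 7 against 14. For the 0–12 month change it is 0. On the other side, Section 2 describes minimum acceptable diet for ages 6–23 months, and Section 4 enrols at 6–24 months. If enrolment ages are uniform, the share who have reached 24 months is 6/18 = one third at the 6-month visit, 12/18 = two thirds at 12 months, and all at 18 months.

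**The case against.** The strongest reply is that this is a pilot and says so. The non-random control group and the reason for it are open in Section 3, and Section 13 calls the effect size initial and defers to better-controlled studies. A reader might infer from the gaps that the plan places no limit at all on interpretation. The documents do not support that: a general caution is there. Only the specific statement, that garden and site are inseparable, is missing.

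A reader might also infer that the team intends two within-group tests in place of a comparison. The sentence says that changes are compared between groups, covers binary and continuous outcomes, and names regression. A chi-square test on improved, unchanged or worsened by group would also be a valid comparison of change. What stands is that one listed method cannot answer the stated question and that the choice among the rest is open.

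The sizes are also open to challenge. No passage gives an ICC, the number of communities, a seasonal swing or unequal enrolment pace. The seasonal figures are not bounds: a step-shaped lean season of 4 months gives up to 0.57 × S (7 against 14 months) and 0.30 × S (8 against 10). These objections limit the numbers but leave the gap in the text.

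**Conclusion.** The point holds on the text. Group and site coincide without randomisation. The list of methods for comparing groups includes one that tests change within a group. No regression of change is fixed, no use of baseline age or poverty score is stated, and nothing allows for community.

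The documents do not fix how large the resulting bias or over-precision is. Under the assumed inputs the error of a naive 5% test runs from 5.5%, nearly harmless, to about 16%. If there is only one community per group, the clustering cannot be estimated or corrected. It would be wrong to conclude that the two sites do differ, that the estimate will be biased in a known direction, or that season will distort it: with equal enrolment pace, or at 12 months, the common yearly cycle assumed above cancels. The appendices are not shown and could already record community.

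**What to change.** In Section 13:

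1. Make the main between-group analysis a regression of the within-child or within-household change on study group, adjusted for baseline child age and poverty score, with robust standard errors, at one visit named in advance. If change in a binary indicator is coded −1, 0 or +1, the result is a difference in change of prevalence in percentage points. In choosing the visit, weigh season against the age range of the child feeding indicators. Report the unadjusted difference in change and a baseline-outcome-adjusted estimate as sensitivity analyses. Use paired t-tests only to describe change within a group. Add calendar-timing terms only if the chosen visit is not 12 months after baseline and enrolment timing differs between sites.
2. Record a community code for each family. With several communities per group, report cluster-robust intervals with a small-sample correction (for example CR2 with Satterthwaite degrees of freedom) and the ICC. With one per group, state that clustering cannot be corrected.
3. State that the estimate is a difference between two sites, that its interval excludes between-site variation, and that it should not alone serve as the garden effect size for a later trial.

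**Cost.** One code per family and analysis wording; no new visits or instruments. Timing terms, where used, widen the simulated standard error by about 4–5% at 8 against 10 months of recruitment and 12–13% at 7 against 14. Clustering can cost far more: with 2 communities per group there are about 2 degrees of freedom, and the critical value alone widens the interval by 4.30/1.98 = about 2.2 times. Three estimates may differ and need explaining, and the conclusion will be more guarded.

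### The adopter versus non-adopter comparison is raw, so self-selection may bias it and it could be misread as evidence of a garden effect

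*Combined protocol and SAP*

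**What the plan says.** Section 13 plans two analyses inside the intervention group. The first concerns who adopts: "Within the intervention group, the rate of overall adoption will be compared descriptively across various demographic groups". The second concerns outcomes: "changes in primary and secondary outcomes will also be compared descriptively between adopters and non-adopters". No test, model, covariate or guidance on interpretation is attached to the second.

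The garden question itself is handled elsewhere in Section 13, where changes in outcomes are "compared between study groups using the chi-square test, paired t-tests (or the non-parametric equivalent) and linear and logistic regression as appropriate". The study is presented as a pilot meant to "generate an initial effect size estimate for future, well-controlled studies".

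Three other places bear on the point:
- Section 12 lists the data. Diet indicators, food insecurity, poverty score and crop inventory are collected from all families at 0, 6, 12 and 18 months. The agronomist records gardening experience and motivation at the first agricultural visit. Adoption and garden upkeep are recorded about 4 months later.
- Section 6 gives the 6-month nutrition programme to both groups, so adopters and non-adopters alike receive it.
- Section 19 expects the implementation evaluation to be informative, "giving valuable insights into how and why the intervention achieved the level of success that it did".

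**The concern.** Adoption is not assigned. It is a behaviour observed after enrolment, and families who adopt may differ from those who do not in engagement, motivation, poverty or food insecurity. Any of these could also affect how diet changes. The nutrition programme offers a concrete route: Section 2 reports that it raised child minimum dietary diversity and minimum acceptable diet in an earlier randomised trial. Families who follow advice closely could both keep a garden and gain more from the nutrition teaching. Section 15 adds a second route. Families who leave the garden component or nutrition care are still measured if they agree, so low engagement could gather among the non-adopters.

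Comparing changes does not settle this. Subtracting the starting value leaves regression to the mean. With yes/no indicators, a family that already meets the criterion at baseline cannot improve.

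What is at stake is interpretation. The main comparison has one non-randomised area per arm (Section 3). In the text supplied, the adopter contrast is the only comparison of outcomes between families within one study area. A reader wary of site differences could give it more weight than it can bear.

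**Working it through.** **The plan's own figure.** There is none to reproduce. Section 13 says "As such no formal power analysis will be performed". The only check is enrolment in Section 5: 70 + 70 = 140, which agrees.

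**Inputs from the documents**
- 70 intervention families (Section 5).
- 16.9 points: the risk difference for minimum dietary diversity in the earlier trial of the nutrition programme (Section 2). It is a between-arm difference, not a gain measured per family, and is used here only for scale.

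**Assumed inputs**
- The garden effect is zero.
- Half the families are highly engaged (E).
- Engaged families gain d points more than the rest.
- Adoption is more common among engaged families.

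**Formula.** Spurious difference = d × [P(E | adopter) − P(E | non-adopter)].

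**Step 1: size of d.** Split the gain as 1.5 × 16.9 = 25.35 in the engaged half and 0.5 × 16.9 = 8.45 in the rest. The mean is 16.9 and the gap is d = 25.35 − 8.45 = 16.9.

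**Step 2: spurious difference for three assumed pairs of adoption rates.** Overall adoption is 60% in each.

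| Adoption, engaged / other | P(E, adopter) | P(E, non-adopter) | Spurious difference |
|---|---|---|---|
| 70% / 50% | 0.35/0.60 = 0.583 | 0.15/0.40 = 0.375 | 16.9 × 0.208 = 3.5 |
| 80% / 40% | 0.40/0.60 = 0.667 | 0.10/0.40 = 0.250 | 16.9 × 0.417 = 7.0 |
| 90% / 30% | 0.45/0.60 = 0.750 | 0.05/0.40 = 0.125 | 16.9 × 0.625 = 10.6 |

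**Step 3: a second parameterisation.** Take 50% adoption and an engagement–adoption odds ratio (OR). Then P(E | adopter) = √OR/(1 + √OR), and P(E | non-adopter) is its complement.

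| OR | Difference in P(E) | d = 8.45 | d = 16.9 | d = 33.8 |
|---|---|---|---|---|
| 1 | 0 | 0 | 0 | 0 |
| 2 | 0.172 | 1.4 | 2.9 | 5.8 |
| 4 | 0.333 | 2.8 | 5.6 | 11.3 |
| 9 | 0.500 | 4.2 | 8.4 | 16.9 |

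The value d = 33.8 puts the whole average gain in the engaged half (33.8/2 = 16.9). If adoption were instead more common among less engaged families, the signs would reverse.

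**Step 4: precision.** With 35 versus 35 families and proportions near 0.5, the 95% half-width is 1.96 × √(0.25/35 + 0.25/35) = 1.96 × 0.1195 = 0.234, or about 23 points. With 21 versus 49 it is 1.96 × √(0.25/21 + 0.25/49) = 0.256, or about 26 points. This treats the indicator at one time point. For a within-family change the variance is 2 × 0.25 × (1 − r), where r is the correlation between visits. It equals 0.25 at r = 0.5 and is larger for weaker correlation.

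**Step 5: how often the contrast would mislead.** Take d = 16.9 and 35 versus 35 families. A garden with no effect would show adopters ahead in about 60% of studies at OR 2 and 76% at OR 9, against 50% with no confounding. A two-sided 5% test, which is not planned, would be significant in about 6% to 11% of studies. In the most extreme case examined (d = 33.8, OR 9) it would be significant in 30%.

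**The case against.** The strongest reply is that the plan makes no claim from this contrast. It is descriptive, carries no test, and sits beside a between-group comparison that addresses the garden and allows regression. That stands. A reader might infer that the plan would make a useless garden look proven. The documents do not support that, and Step 5 shows that a null garden would not reliably appear effective. A descriptive label limits testing, however. It does not remove bias from the difference that is displayed.

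Other parts of the reply also hold:
- Comparing changes takes some account of starting values.
- Section 2 documents significant programme gains in child minimum dietary diversity, minimum acceptable diet and some food groups. The growth effect was not significant, and no effect is given for food insecurity, caregiver diet or crop diversity. The nutrition-programme route is therefore documented for only part of the endpoint set.
- No document links engagement with adoption. Need or poverty could push adoption in either direction, so the sign of the bias is not established.
- The Section 19 sentence concerns factors affecting implementation. Section 3 draws that evaluation from programme records, surveys, focus groups and interviews. A reader might infer that it rests on the adopter contrast, but neither section says so.
- Adoption will be described by demographic group, and motivation is recorded. Appendices I and J were not available, so an adopter definition or interpretive guidance there cannot be excluded.

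**Conclusion.** The point holds as a cheap improvement to an exploratory analysis, not as a flaw in the main comparison. As written, the contrast is raw, adoption is self-selected after enrolment, and nothing in the text supplied warns against a causal reading. The bias probably favours the garden, but this is not certain.

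With d = 16.9 and half the families engaged, the spurious difference is roughly 3 to 11 points. Across all the values tried it runs from 0 to 16.9. Apart from the 16.9-point scale and the 70 families, every input is assumed. The 3 to 11 points lie well inside the sampling uncertainty of about 23 points. The practical risk is therefore a misleading direction or point estimate, not a false positive test.

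**What to change.** Amend Section 13 as follows:
1. Tabulate by adoption status the baseline diet indicators, food insecurity, poverty score and crop diversity, together with gardening experience and motivation. Cite the definition of an adopter, or state one if the appendices lack it. Include nutrition-programme attendance as description only, and only if it is available: it is not in the Section 12 data list, and Section 21 denies study personnel access to the medical record.
2. Beside the raw contrast, report one adjusted for the baseline value of the outcome and the baseline poverty score, with a confidence interval. Do not adjust for attendance in this main adjusted contrast. It is measured after enrolment and could itself be affected by the garden programme.
3. State that the contrast is an exploratory association and not evidence of a garden effect.

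Setting adopters beside control families with similar characteristics is tempting but should not be added, nor should any rule that credits or discredits the garden on that basis. All controls come from another area, so site differences would return.

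The cost is one table, one adjusted model per outcome and one sentence, with no new participants or visits. The downside is wider intervals with at most 70 families. Adjustment reduces confounding by the measured variables, but residual confounding will remain.
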